## 9. Data collection, handling and quality assessment

In accordance with Danish law on personal data, we have approval for this trial from Region Sjælland through their data application system (REG-106-2020). Data handling will be in accordance with legislation on the processing of sensitive personal information, the GDPR (General Data Protection

Regulation) and the Data Protection Act. We will also seek approval for the trial from The National Committee of Health Research Ethics and the Danish Medicines Agency.

Data from each patient will be recorded continuously and written in forms prepared before the trial begins. Appendix 3-6 and 8 are considered CRF on which source data is directly recorded. During the recruitment meeting, we will use paper work sheets for baseline data and inclusion/exclusion criteria. During the therapeutic endoscopy, we will use paper work sheets for data collection; afterwards data will be entered into an electronic database using the Easytrial platform. All other data will be recorded directly to the electronic Easytrial database. The paper work sheets will be stored in an identifiable manner in a locked cabinet at the respective research sites. All collected data will have source documentation.

Data will be stored as personally identifiable for 10 years, after which they are deleted on December 31, 2030. Data will be stored in compliance with GDPR and at EasyTrial (secure data storage). According to the Danish Medicines Agency, data from a clinical trial involving study medicine, must be stored for a minimum of 5 years after conclusion of the trial. This is necessary in case a potential reexamination of the data is needed.

If a patient withdraws from the study, the collected data will be anonymized. If the patient requests the collected data to be deleted, this will be done.

Data will be handled by [name] and [name] and access to EasyTrial will be restricted solely to them. The investigators will be allowed direct access to data and documents, among these the patients' medical records.

The trial will be monitored by the Good Clinical Practice Unit of the University of Copenhagen. During the duration of this trial, they will also have access to the data we collect. Similarly, the Danish Medicines Agency, according to section 90(2)-5 of the Danish Medicines Act, and The Danish Data protection Agency can conduct inspection visits and get access to the data.

When the handling of data has been completed, the sponsor role and responsibilities will be assigned to Reponex Pharmaceuticals A/S ([name]). The completion of data handling is defined as either the completion of the PhD of [name] or the submission of an article to a journal. The date of this assignment will be communicated to the authorities (Research Ethics Committee, Danish Medicines Agency) when it is known. The data they receive will be pseudo-anonymized. The key-files to the pseudo-anonymization will be kept on separate secure data sites according to GDPR in their region. During and after the assignment, the data handling will be in accordance with legislation on processing of sensitive personal information, the GDPR and the Data Protection Act.

#### **Data from patients' files**

The data collected from patients- files consists of demographic data (age, gender, BMI, comorbidities, WHO performance score, ASA class, history of smoking, medication, date of diagnosis with ulcerative colitis, date of pouch surgery, previous pouchitis treatment. We will collect data on the clinical findings, biochemical findings and PDAI index pre- and post-intervention as well as histology and biofilm results. Patient files will be accessible for reading by authorized personnel until 12 months after the intervention. Before informed consent is obtained from each patient, the following data are necessary for screening of patients by the researchers, which are readily available in a clinical setting:

Protocol code no: 2020-01-GMF-1  
EudraCT no: 2020-000609-10

- Demographic data: age, gender, CPR-number, ASA score, diagnosis of ulcerative colitis, surgical history, diagnosis of pouchitis
- Previous endoscopy data

All other data will be collected after informed consent has been given.

- Data from the therapeutic endoscopy and control endoscopy

Informed written consent by the subject will give the responsible researchers, the sponsor and the supervisory authority access to the patient's electronic health records. This is necessary to assess the subjects' health when conducting the research project, as well as to ensure quality control and monitoring of the project itself.

### **Storage of biological material**

During the trial, biological material will be stored in a research biobank especially set up for this study. The use of a research biobank is to ensure that differences in analyses from patient to patient will be minimal. The research biobank will be reported to the Region Sjælland, and will be maintained using their regulations.

The biopsies are each 2 mm in diameter. The biological material will be stored in an identifiable fashion through a patient code (pseudo-anonymous, as the CPR (Civil Person Registry) number will be stored in a key-file at EasyTrial). Frozen samples will be stored according to the local protocol.

After the cutting of the FFPE blocks containing the biopsy specimens collected from the pouch, these blocks will be returned to the respective pathological archives. Both the biological material (stained glass slides and FFPE blocks of biopsies) and the key-file will be stored until conclusion of the clinical trial, after which both the key-file and the biopsy samples are destroyed.

### **Good Clinical Practice and quality assessment**

This trial is performed in accordance with the trial protocol and ordinary procedures for quality control and assurance are complied with according to ICH-GCP guidelines. This trial is also in compliance with current laws by health authorities including Danish Medicines Act, §88, section 2, and section 3 and 4 of the Danish executive order on Good Clinical Practice number 744 of June 29, 2006. The trial will be monitored by a Good Clinical Practice unit, Capital Region of Denmark. The existing procedures for quality assurance and control in intervention studies will be followed through a scheduled monitoring agreement at the before the start of phase I, between phase I and II and at the conclusion of phase II. At auditing, monitoring and/or inspection from the Danish Medicines Agency, GCP-unit or from other relevant authorities, these will all be allowed relevant access to the data and information stored. The sponsor is informed in writing by the principal investigator when changes from the approved protocol are made.

## **10. Ethical considerations**

### **Informed consent**

Participation in this trial is entirely voluntary, and the patient will only receive preliminary information from the treating gastroenterologist. The treating gastroenterologist will not be directly involved in the study procedures and interventions, in order to minimize any risk of coercion or undue influence of participants. There will be no waiving of the process of informed consent. In the opinion of the investigator, participants must be capable of understanding the purpose of the trial, as well as the potential risks and benefits.

Study patients are included after they have received oral and written information and after written consent has been obtained. At any time, the patients can withdraw their consent without impairing their relationship to the investigator or the doctors involved and without prejudicing their treatment at the Department. All patients can require further information about the project from the responsible clinician. The process of informed consent is described in more detail in chapter 7.

### **Potential harms and benefits**

A large part of the trial procedures are part of regular examinations and treatment of patients seen in the outpatient clinic for pouchitis. The minimal risk of endoscopy of the pouch, blood samples and antibiotic treatment with metronidazole are part of the standard approach in this patient population. This trial adds an additional endoscopy of the pouch after one week, as well as the local application of GM-CSF and fosfomycin. As the medication has previously been tested in more invasive settings (intravenous, subcutaneous, intramuscular and intraperitoneal) without serious adverse reactions, we consider this additional risk permissible. Phase I of the study will test safety and tolerability of the study drug combination, and only if these results are favorable in terms of risk and safety, will a Phase II trial be initiated.

The potential therapeutic benefit of the study would be identifying a new treatment for pouchitis, as well as a better understanding of the disease itself. As of yet, no gold standard of pouchitis treatment exists. Current treatment consists of repeated high doses of oral metronidazole or ciprofloxacin, of which especially metronidazole can have lasting side effects. Loss of effect can result in the need for reoperation in patients with all its potential risks, and creation of an ostomy.

Previous studies have shown some promise in administering GM-CSF in patients with inflammatory bowel disease, and this study will examine the application with a combination with antibiotics locally in the pouch. If effective, this drug combination could potentially lower side effects both short-term and long-term for patients with pouchitis. If no effect can be shown, results from the study will still contribute to our knowledge of the pathophysiology of pouchitis.

We consider the potential harms of the study both in themselves and in relation to the potential benefits of the trial justifiable, and believe that the gain in knowledge and potential new treatment for future patients warrants this trial. It will contribute to the knowledge on the pathogenesis of pouchitis and whether a combination of GM-CSF and antibiotics given locally has an influence on the inflammation of the mucosa.

### **Standard of care**

Patients will not be experiencing any delay in traditional treatment of pouchitis when participating in this trial. Current waiting times on outpatient clinic visits and endoscopy of the pouch, result in start of antibiotic treatment after a few weeks. If included in the trial, patients receive endoscopy and the trial medicine within two weeks, after which standard treatment of oral metronidazole or ciprofloxacin is

administered. Patients participating in the trial will therefore not be suffering symptoms of pouchitis longer than patients not participating in the trial, and no established effective intervention is withheld.

### **Post-trial access**

Post-trial access to the study drug combination will be dependent on the outcome of this study, as well as further clinical studies to assess efficacy and safety in a larger, potentially, randomized placebo-controlled trial.

### **Choice of study design**

The study design is aimed at being a proof-of-concept study, in which it was decided by the sponsor and investigators, that a Phase I of the trial will include 6 patients, and a potential Phase II of the trial 12 patients. Any results from the study will not be able to definitively answer questions of efficacy of the treatment, but will support development of further trials and research into pouchitis. The number of patient visits was chosen to minimize the burden on the participants, while at the same time ensuring patient safety. Follow-up by telephone calls was decided, whenever this was possible.

### **Choice of study population**

The participants studied in this trial all suffer from pouchitis, as diagnosed by a gastroenterologist with experience in the field. Participants are representative of the population that most likely will benefit from results of the study. No healthy volunteers will be studied in this trial, as this is not possible. The study drug combination has previously been tested in healthy males with appendicitis, but not in patients with inflammatory bowel disease or pouchitis. GM-CSF on its own, has been previously tested in individuals with Crohn's disease, while metronidazole has been used extensively in pouchitis.

The patients will be informed of any additional health information found in the study.

### **General considerations**

The study is performed in accordance with the Helsinki Declaration and Danish law 593 of June 14, 2011, on the Research Ethics Committee's practices regarding health research trials. The project has been approved by the departmental management, Region Sjællands data application system (REG-106-2020), the Regional Research Ethics Committee (conditional approval, application no: 75784 ), and the Danish Medicines Agency (conditional approval). The study is registered at the EudraCT (2020-000609-10) and will be registered at [www.clinicaltrials.gov](http://www.clinicaltrials.gov). The trial will be monitored by the local GCP Unit. Any modification of the protocol which may impact the conduct of the study, potential benefit of the patient or may affect patient safety, including changes of study objectives, study design, patient population, sample sizes, study procedures, or significant administrative aspects will require a formal amendment to the protocol. An amendment will be agreed upon by the study group and will need approval by the Ethics Committee and other authorities as appropriate, prior to implementation.

The study will be conducted in the Department of Surgery of Zealand University Hospital.

## **11. Funding and insurance**

[name] DMSc (sponsor) and [name] MD (principal investigator) initiated this project. The investigators and the sponsor have no financial interests or conflicts of interest in this study. Reponex Pharmaceuticals A/S ([name]) will distribute the trial drugs to the participating department as well as cover salary expenses for [name] and the running costs of the trial. The funding source had no role in the design of this study and will not have any role during its

execution, analyses, interpretation of the data, or decision to submit results. The funding is an unrestricted grant to the research unit of 2.3 million DKK. After completion of the trial Reponex Pharmaceuticals A/S will be assigned the sponsor role and its responsibilities.

Information about external funding is included in the written information for the patients. Any external funding will be reported to the Research Ethics Committee with information of the amount and the contributors' names. The written information for the patients will also be updated. There will be no fees for trial participation. Participants will not receive payment for participation, but will get their transportation to treatment refunded, including a taxi from or to work or their home. Also, oral metronidazole or ciprofloxacin for 10 days, the current treatment for pouchitis, will be provided to the patient for free after the second endoscopy.

Patients experiencing injury or harm due to study treatment are covered by the already existing insurance for hospitalized patients in the Department of Surgery, Zealand University Hospital (Patient Insurance Scheme). This is according to the 'Danish Act on the Right to Complain and Receive Compensation' chapter 3, paragraph 19, clause 3: *'Individuals who take part in health research, including clinical trials with drugs, that is not part of the diagnosis or treatment of the individual's disease or illness, are considered equal to patients. This also applies to patients from whom tissue and other biological material is taken.'*

## 12. Publication of research findings

Following completion of the study, the positive, negative or inconclusive results of this research will be published in an international peer-reviewed scientific journal. Authorship eligibility will be based on the guidelines of the ICMJE (International Committee of Medical Journal Editors).

The Research Ethics Committee and the Danish Medicines Agency will be informed within 90 days when the last patient has had their last visit, and a final report will be submitted within 12 months to the EUDRACT database (European Union Drug Regulating Authorities Clinical Trials database).

## Appendices

### Appendix 1 – PDAI

Criteria	Score
Clinical	
Stool frequency	
Usual postoperative stool frequency	0
1–2 stool/day >postoperative usual	1
≥3 stools/day >postoperative usual	2
Rectal bleeding	
None or rare	0
Present daily	1
Faecal urgency or abdominal cramps	
None	0
Occasional	1
Usual	2
Fever (temperature >37.8°C)	
Absent	0
Present	1
Endoscopic inflammation	
Oedema	1
Granularity	1
Friability	1
Loss of vascular pattern	1
Mucous exudate	1
Ulceration	1
Acute histological inflammation	
Polymorphonuclear leucocyte infiltration	
Mild	1
Moderate+crypt abscess	2
Severe+crypt abscess	3
Ulceration per low power field (mean)	
<25%	1
25–50%	2
>50%	3

Table 1: Pouchitis Disease Activity Index (PDAI). A score of 7 or higher is diagnostic of pouchitis.

## Appendix 2 – Study schedules

### Phase I Study Schedule

		Follow-Up Schedule			
Procedures		Screening Day 0	Baseline Day 1	Follow-up Day 7	Follow-up Day 30
Signed Consent Form		X	X		
Assessment of Eligibility Criteria		X	X		
Review of Medical History		X	X		
Review of Concomitant Medications		X	X	X	X
Application of study drug			X		
Physical Examination	Complete	X		X	
	Symptom-Directed		X		
	Vital Signs		X	X	
Assessment of Adverse reactions			X	X	X
Clinical Laboratory	Chemistry	X		X	
	Hematology	X		X	
Histology	Endoscopy with Biopsies		X	X	
Microbiology			X	X	

Phase II Study Schedule

				Follow-Up Schedule		
Procedures		Screening Day 0	Baseline Day 1	Hospital administration Day 2-7	Follow-up Day 14	Follow-Up Day 37 (1 month after treatment)
Signed Consent Form		X	X			
Assessment of Eligibility Criteria		X	X			
Review of Medical History		X	X			
Review of Concomitant Medications		X	X		X	X
Application of study drug as enema			X	X		
Physical Examination	Complete	X			X	
	Symptom-Directed		X			
	Vital Signs		X		X	
Assessment of Adverse reactions			X	X	X	X
Clinical Laboratory	Chemistry	X			X	
	Hematology	X			X	
Histology	Endoscopy with Biopsies		X		X	
Microbiology			X		X	

### Appendix 3 – Enrollment form

Name:

Address:

Telephone no:

Date of birth
Gender
Year diagnosed with ulcerative colitis
Year of IPAA surgery
Allergies
Past medical history  COPD  Others  Diabetes  Asthma  Hypertension  Ischemic heart disease  Liver disease  Neurological diseases
Medicine
Past medicine used for pouchitis  Metronidazole  Ciprofloxacin  Ampicillin  Piperacillin  Probiotics  Others
Diets used for pouchitis

Protocol code no: 2020-01-GMF-1  
EudraCT no: 2020-000609-10

Clinical PDAI to be filled in at enrollment:

Criteria	Score	Patient score
Clinical		
Stool frequency		
Usual postoperative stool frequency	0	
1-2 stools/day > than postoperative usual	1	
>3 stools/day > postoperative usual	2	
Rectal bleeding		
None or rare	0	
Present daily	1	
Fecal urgency or abdominal cramps		
None	0	
Occasional	1	
Usual	2	
Fever (temperature > 37.8)		
Absent	0	
Present	1	
Total	6	

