### **Bias**

This study is an open-label proof-of-concept study with a single treatment arm. There is no blinding of patients or the investigator. The only blinded examination is the pathology examination of mucosal biopsies of the pouch and 16S rRNA sequencing. The pathologist is unaware of whether samples are taken before the application of the study drug or after. Therefore, the histology of the PDAI should not be influenced by bias.

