## Appendix 7 – Patient PDAI overview

Patient name:

Criteria	Score	Patient score before treatment Date:    /    /   	Patient score after treatment Date:    /    /   
Clinical			
Stool frequency Usual postoperative stool frequency 1-3 stools/day > than postoperative usual >3 stools/day > postoperative usual	0 1 2		
Rectal bleeding None or rare Present daily	0 1		
Fecal urgency or abdominal cramps None Occasional Usual	0 1 2		
Fever (temperature > 37.8) Absent Present	0 1		
Endoscopic inflammation Edema Granularity Friability Loss of vascular pattern Mucous Exudate Ulceration	1 1 1 1 1 1		
Acute histological inflammation Polymorphonuclear leucocyte infiltration Mild Moderate + crypt abscess Severe + crypt abscess Ulceration per low power field (mean) <25% 25-50% >50%	1 2 3 1 2 3		
Total	18		

Date                      Place

Examiner:

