Appendix 8 – Follow-up Day 7/14/(30/37)

Name:

Side effects:		
GM-CSF  Fever  Myalgia  Malaise  Abdominal pain  Diarrhea  Rash  Chest pain  Weight loss  Nausea  Vomiting  Peripheral edema  Dyspnea  Hypoxemia  Hypotension  Tachycardia  Flushing  Metabolic disease  Hyperbilirubinemia  Cardiac dysrhythmia  Pharyngitis	Metronidazole  Nausea  Glossitis  Dry mouth  Dysgeusia  Stomatitis  Myalgia  Candida-infection  dark urine	Fosfomycin  Phlebitis  Vomiting  Abdominal pain  Diarrhea  Rash  Fatigue  Dysgeusia  Decreased appetite  Vertigo  Headache
Adverse reactions           		
Serious adverse reactions / Life-threatening adverse reactions  Capillary leak syndrome           		

Protocol code no: 2020-01-GMF-1  
EudraCT no: 2020-000609-10

Clinical PDAI to be filled in at follow-up:

Criteria	Score	Patient score
Clinical		
Stool frequency		
Usual postoperative stool frequency	0	
1-4 stools/day > than postoperative usual	1	
>3 stools/day > postoperative usual	2	
Rectal bleeding		
None or rare	0	
Present daily	1	
Fecal urgency or abdominal cramps		
None	0	
Occasional	1	
Usual	2	
Fever (temperature > 37.8)		
Absent	0	
Present	1	
Total	6	

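### The PDAI stool item is an excess over the patient's usual frequency, but no printed form requires that usual number or the current count, and the protocol does not say the baseline reference is reused

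*Protocol*

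**What the plan says.** Appendix 1 of the Protocol defines the stool item as an excess over the patient's postoperative norm: 0 for no excess, 1 for an excess of 1 or 2 stools/day, and 2 for "≥3 stools/day >postoperative usual".

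The enrollment form (Appendix 3) repeats the item. It has the reference category "Usual postoperative stool frequency", then "1-2 stools/day > than postoperative usual" for 1 point and ">3 stools/day > postoperative usual" for 2. The follow-up form (Appendix 8) prints "1-4 stools/day > than postoperative usual" for 1 point, and the overview form (Appendix 7) prints "1-3 stools/day > than postoperative usual". All three forms provide only for the patient's score. None has a field for the usual or the current number of stools per day.

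Section 9 makes the enrollment and follow-up forms the primary record: "Appendix 3-6 and 8 are considered CRF on which source data is directly recorded". The list of collected data in the same section (Data from patients' files) names clinical findings and the PDAI before and after treatment, but no stool count. Section 7 (Clinical evaluations) calls for a full history at baseline, from interview and health records, and for the history and PDAI to be updated at later visits. It does not say whether the reference used at baseline is used again.

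Section 3 makes a PDAI fall of 3 points or more the improvement criterion for the Phase II primary outcome. Its Bias paragraph states: "There is no blinding of patients or the investigator".

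**The concern.** The item is a difference between two numbers, and the forms require neither. If the reference is stated differently at the two visits, the score can change although the patient passes the same number of stools. From the forms alone, that change cannot be told apart from a change in disease.

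This bears on the Phase II primary outcome. There is no control arm in which the same drift would show, and both the patient and the person scoring know that treatment has been given. The Bias paragraph relies on blinding for histology and sequencing only, so the clinical items have no such protection.

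A statistical analysis plan cannot repair this. If the 0, 1 or 2 is the only thing written on the source form, the counts cannot be derived from it later.

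**Working it through.** **Inputs.** The item bands come from Appendix 1, the 3-point criterion from section 3, the score totals from Appendices 3 and 7, and the Phase II numbers (12 planned, 9 stated as needed) from section 8. The stool counts and reference shifts below are illustrative assumptions, because the protocol gives none.

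**The plan's own totals.** The clinical part is 2 (stools) + 1 (bleeding) + 2 (urgency or cramps) + 1 (fever) = 6, as Appendix 3 prints. Adding 6 endoscopic and 6 histological points gives 18, as Appendix 7 prints. The stool item is therefore 2 of 18 points overall and 2 of 6 in the clinical sub-score, which has its own 3-point criterion among the Phase II secondary outcomes.

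**Scoring rule.** Let e be the excess (current count minus reference). Under Appendix 1, S(e) = 0 if e ≤ 0, 1 if e is 1 or 2, and 2 if e ≥ 3. Hold the count fixed and raise the stated reference by d. The artificial fall is S(e) − S(e − d).

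*Example.* Take 9 stools/day at both visits. A reference of 6 gives e = 3 and score 2. A reference of 7 or 8 gives e = 2 or 1 and score 1. A reference of 9 gives e = 0 and score 0.

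| Baseline excess e | Baseline item | Fall, d = 1 | d = 2 | d = 3 | d = 4 |
|---|---|---|---|---|---|
| 1 | 1 | 1 | 1 | 1 | 1 |
| 2 | 1 | 0 | 1 | 1 | 1 |
| 3 | 2 | 1 | 1 | 2 | 2 |
| 4 | 2 | 0 | 1 | 1 | 2 |

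- **Two-point fall.** This needs e ≥ 3 at baseline and e − d ≤ 0 at follow-up, so d ≥ e ≥ 3.
- **One-point fall.** A shift of one stool is enough when e is 1 or 3.
- **Opposite direction.** If the stated reference drops, the score rises. From e = 0, a drop of 1 or 2 adds 1 point and a drop of 3 adds 2.

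**Against the criterion.** The artefact is at most 2, and 2 < 3, so it cannot produce an improvement alone. A true fall of 2 plus an artefact of 1 gives 3, as does a true fall of 1 on other items plus an artefact of 2. Conversely, a true fall of 3 less an artificial rise of 1 gives 2, and the improvement is lost. One patient misclassified either way moves the observed improvement proportion by 1/12 = 8.3 percentage points, or 1/9 = 11.1 points if 9 are analysed.

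**Why the printed forms do not allow re-scoring.** With the count and the reference both unchanged, the printed bands give:

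| Excess | App. 1 | App. 3 | App. 7 | App. 8 |
|---|---|---|---|---|
| 1 or 2 | 1 | 1 | 1 | 1 |
| 3 | 2 | no band | 1 | 1 |
| 4 | 2 | 2 | 2 | both 1 and 2 |
| 5 or more | 2 | 2 | 2 | 2 |

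The differing bands are a separate error. They matter here because recorded counts would let every score be derived again on one set of bands, whereas a recorded 0, 1 or 2 does not.

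**The case against.** The relative wording belongs to the index itself, and the forms reproduce the instrument and record its item score. Asking for the raw numbers is an addition to that. Section 7 speaks of updating the PDAI after a history drawn partly from health records, which may mean that the baseline reference is kept. Section 9 promises source documentation for all collected data, so the usual frequency may be in the patient's file. The worst case needs a shift of 3 stools/day between baseline and a follow-up at day 6–9 (Phase I) or day 13–16 (Phase II). Twelve of the 18 points are endoscopic or histological, and histology is read blind. The protocol discloses the open-label limitation and says that the results cannot settle efficacy.

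Most of this stands, and it limits the point in three ways.

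- A reader might infer that the reference is recalled afresh at every visit. The protocol does not say so; it is silent on whether the reference is reused.
- A reader might infer that nothing on file could ever verify the score. The documents support only that no printed form requires the number.
- A reader might infer that the artefact favours the treatment, or creates responders at some rate. The documents give no direction and no frequency.

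The objection does not remove the gap. No form or instruction asks for the two numbers behind the score, or for one reference at both visits.

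**Conclusion.** The point holds in a limited form and is worth correcting before data collection. The forms neither record the inputs of the stool item nor fix its reference. An unchanged stool count can therefore yield a different score, and the printed forms give no means of detecting or re-scoring it.

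The size is a ceiling of 2 points in either direction on the Appendix 1 cut-offs, and a 2-point fall requires a reference shift of at least 3 stools/day. This is too little to meet the 3-point criterion alone, but enough to push a true fall of 1 or 2 points over it or to mask a true fall of 3. The result assumes that the reported reference can differ between visits, which the protocol neither prevents nor documents. No false-response rate can be given, and no sample-size figure changes.

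**What to change.** Add to Appendix 3 a numeric field for usual postoperative stools/day, completed once before dosing, and one for current stools/day. Add current stools/day to Appendix 8. State that the item at both visits is derived from these counts against the single reference fixed at enrollment. First reconcile the bands in Appendices 1, 3, 7 and 8, because the derivation rule needs one set of cut-offs.

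The cost is about three form fields and one derivation rule, with no extra visit or procedure. The current stool count would still be unblinded self-report, so this removes one route of bias and leaves the others.
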